All patients on drug treatment will enter a 2-week wash-out and safety follow up period following end of the Treatment Period with procedures conducted according to the Schedule of Events (See [Appendix 1](#)).

Patients with a Worst Itch NRS score less than 5 (< 5) enter the Observation Period:

Patients with a Worst Itch NRS score < 5 at Visit 1a will enter into an extended screening period, Observation Period (no drug treatment), of the study and will be followed for up to 12 weeks (extended screening weeks). Visit 1a for these patients is also Observational Visit 1 (OV1). Subsequent visits will be defined as OV2, OV3 and OV4 and will occur at approximately monthly intervals for the next 3 months.

During this Observation period, patients who report an increase in their Worst Itch NRS with a score of ≥ 5 at any one of their Observation Visits and meet all other eligibility criteria will be able to enroll immediately into the Treatment Period of the study and Visit 1b procedures are to be performed. Patients will receive open-label Study Drug starting with an evening 30 mg dose (to be taken at home), after the Visit 1b procedures have been completed. Receipt of the first drug will indicate the start of their Treatment Period and enrollment into the study. The duration of the Treatment Period for such a patient will vary depending upon the visit at which they transition from the Observation Period to the Treatment Period.

Patients in the Observation Period whose Worst Itch NRS score remains <5 over the 12 extended screening weeks will be screen failed from the study at the end of that time period.

Failure to Improve Criteria:

Beginning on TV 3 and at every subsequent Treatment Visit, patients with a Worst itch NRS equal to or greater than (\geq) the Worst Itch NRS at Visit 1a (or at Visit 1b in the case of patient who require the Observation Visit period) will be discontinued from taking study drug. Subjects discontinued from taking study drug are to undergo the End of Treatment Visit (TV14), the Washout/Safety Follow-up Period assessment in two weeks and receive a follow-up Telephone Contact 30 days following end of study drug for final safety

	assessment.

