9.2 RATIONALE FOR STUDY DESIGN

The primary objective of this TR03ext study is to evaluate the safety of nalbuphine HCl ER tablets in patients with prurigo nodularis for up to 50 weeks on drug, followed by a two week washout period for a total of up to 53 weeks of study duration. The open label design allows all patients, who have completed the parent study TR03, an opportunity to receive active treatment for the assessment of the safety of nalbuphine HCl ER tablets over a longer term and follow the effect of skin lesion healing in addition to reducing itch. A maximum of 50 weeks on study drug was chosen as a reasonable time frame that would add substantially to the understanding of chronic use of nalbuphine HCl ER tablets chronic use in prurigo nodularis.

Metze et al (1999) reported that 9 out of 17 patients with PN who were treated with the mu antagonist medication naltrexone reported a decrease in pruritus intensity of at least 50%.

Reduced scratching as well as skin lesion healing was reported over a time period of up to 20 months on drug. Based on these clinical observations, TR03ext was designed to be of sufficient duration to observe potential anti-pruritic suppressive effects of study drug on scratching behavior and thus potentially skin lesion healing. Furthermore, the TR03ext study design anticipates potential sustained anti-pruritic effect that may outlast the actual dosing of study drug in TR03. Thus an Observation Period has been incorporated to follow patients whose Worst Itch NRS has been significantly reduced for up to 12 weeks in order to measure the durability of the anti-pruritic effect and to allow patients to receive study drug if pruritus intensity increases within the 12 week time period.

This study will also allow evaluation of a titration algorithm that mimics the manner in which opioid medications are often used in clinical practice (i.e., stepwise titration) to a tolerable dose with an improvement in worst itch intensity. To facilitate evaluation by achieved dose, the dose to which the patient has been titrated at the end of Treatment Week 4 will be maintained through Study Week 50, with the exception of two allowable down-titration (See [Table 3](#) for dosing schedule). Patients who require a third down-titration after Treatment Week 4 must be discontinued from the study.

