Patients can enroll into TR03ext and receive drug as early as approximately 2 weeks following their last dose of study drug in the parent study TR03. Approximately one-third of patients are expected to enter the study after having received placebo in TR03. These patients are expected to have a high level of pruritus intensity. On the other hand, some patients who have received active treatment in TR03 may still have either reverted to their original pruritic conditions or may have a residual anti-pruritic effects from the drug treatment even following the 2-week wash out period. To allow for various starting levels of pruritus intensity, patients who have Worst Itch NRS that is ≥ 5 will enter the Treatment Period upon completion of Visit 1a. Patients whose Worst Itch NRS score is < 5 will be entered into an extended screening period, no-treatment criteria Observation Period for up to 12 weeks or until they develop a higher level of pruritus (i.e., Worst Itch NRS ≥ 5), at which point they will transition to the Treatment Period upon completion of Visit 1b. All patients entering the Treatment Period, whether immediately upon study entry or following a period of time in the Observation Period, will initially be titrated to a dose that can be as high as 180 mg BID during the first 4 weeks of the Treatment Period (See [Table 3](#) for dosing schedule). Patients who continue in the Observation Period and maintain a Worst Itch NRS score of < 5 will be screen failed from the study at the end of the 12-week period. While patients remain in the Observation Period, they will not be considered as enrolled into the study, but as participating in an extended screening process until they are eligible for treatment.

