Patients who fail to improve, as defined by the failure-to-improve criteria, will be taken off study drug treatment. A failure-to-improve criteria is implemented beginning on TV 3 and at every subsequent Treatment Visit, and is described in [Section 11.1](#). The rationale for the failure-to-improve criteria is based on the following: Following a maximal titration period of up to 3-weeks, an approximate 2-week window on stable drug dose should be sufficient for the drug to start eliciting a beneficial effect. The subject's self-reporting of pruritus intensity at each visits beginning at TV 3 will be compared to the baseline value of the patient's pruritus intensity upon entry to TR03ext. The premise of the failure-to-improve criteria is that patients will not be allowed to continue to receive study drug for an extended

period of time if there is no demonstration of diminishment in pruritus intensity. Subjects discontinued from treatment are to participate in the Washout and Safety Follow-up Period, unless consent is withdrawn. These patients will also receive a Telephone Contact 30 days (+2 weeks) post the completion of study drug to collect safety information related to previous drug exposure.

In the parent study, TR03, the two target doses (90 mg and 180 mg) of nalbuphine HCl ER are both within the dose range that was well tolerated in HD subjects and healthy volunteers subjects from study TR01 (30 mg to 240 mg BID for up to 15 days). Additionally, data from TR01 suggested a decrease in itching intensity in this dose range. Further, the safety profile of nalbuphine following injection is well documented. Injectable nalbuphine has been commercially available in the United States since 1979 and there has been marketing experience within the European Union dating back to 1986 (See Nalbuphine -Medicines Evaluation Board in the Netherlands Public Assessment Report (2010) for a recent review).

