9.3 SAFETY MONITORING PLAN

Patients will be closely monitored for safety. Adverse events will be continuously evaluated throughout the study (and in particular AEs of special interest: nausea, vomiting, constipation, somnolence, sedation, dizziness, and vertigo) and vital signs, locally and central cardiac core laboratory read 12-lead ECGs, physical examinations, and clinical laboratory testing will be conducted to monitor patient safety.

An independent Data Safety Monitoring Board (DSMB) will periodically review safety data. The frequency of data review and DSMB processes are outlined in the DSMB charter.

Patients with apparent failure-to-improve to a stable dose of study drug will be taken off study drug.

As with all subjects who are discontinued from study drug, the patient will complete a daily SOWS scale for the two weeks following the last dose of study drug. The SOWS is a self-administered scale for grading opioid withdrawal symptoms. If the subject is experiencing any symptoms on the SOW scale to a moderate degree, the subject will be instructed to contact the site. If a subject is determined to be experiencing significant subjective withdrawal symptoms (at the Investigator's discretion), the subject will be offered treatment.

As summarized in Section 6.2.7 of the Investigator Brochure, the CNS has been identified as the only target organ when nalbuphine was given to animals at high doses. In addition, the most frequently reported adverse events reported in the nalbuphine HCl ER tablet dosing studies were primarily in the nervous system and gastrointestinal organ system categories. .

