9.6.2.2.1 TV 3 (Treatment Week 5)

The following procedures are to take place at this visit:

- Administer the Worst Itch NRS and evaluate against the Failure-to-Improve criteria (see [Section 11.1](#))
- For patients who MEET the Failure-to Improve criteria
 - Stop study medication
 - Perform End of Treatment Visit (TV14) procedures
- For patients who DO NOT meet Failure-to-Improve criteria, perform the following procedures
 - obtain vital signs
 - collect urine for pregnancy test (must be confirmed negative prior to dispensing study drug)
 - collect blood for PK
 - perform 12-Lead ECG after at least 5 minutes in a supine position (See the Study Reference Manual for ECG procedures, [section 17.4](#) Electrocardiograms for the handling of Cardiovascular adverse events)
 - perform brief neurological assessment
 - administer PRO measurements:
 - Average itch intensity NRS

- VRS
- ItchyQoL
- MOS Sleep-R
- HADS

The PRO questionnaires must be administered at the study site under the supervision of and by trained study staff, strictly adhering to PRO Administration Instructions (see Study Reference Manual).

- record AEs
- review of concomitant medications, including over-the-counter medications, nutritional supplements, and vitamins
- reinforce compliance
- perform study drug accountability, retrieve previously dispensed study drug
- dispense the study drug to the patient required until the next Treatment Visit

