⁶ Beginning on TV 3 and at every subsequent Treatment Visit, patients with a Worst itch NRS \geq the Worst itch NRS at Visit 1a (or at Visit 1b in the case of patient who require the OV period) will be discontinued from study drug, complete the End of Treatment Visit 14, the Washout and Safety Follow-up Period and Visit, and a Telephone Contact Visit 30 days after the last dose of study drug.

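### The failure-to-improve stop, as stated in the synopsis and Table 3 footnote 6, makes no allowance for a visit that falls in a dose hold or the once-daily restart

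*Protocol*

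**What the plan says.** All references are to protocol Version 2.0 (Amendment 1).

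- **The stop.** The synopsis, under Failure to Improve Criteria, reads "Beginning on TV 3 and at every subsequent Treatment Visit, patients with a Worst itch NRS equal to or greater than" the baseline score, and such patients are taken off drug. Table 3 footnote 6 (Section 9.7.1) repeats the rule: "Beginning on TV 3 and at every subsequent Treatment Visit, patients with a Worst itch NRS" at or above the Visit 1a or 1b score are taken off drug. Neither place sets a condition on current dosing.
- **The visits.** Each of the TV3 to TV13 sections has the step "Administer the Worst Itch NRS and evaluate against the Failure-to-Improve criteria" and refers to Section 11.1. If the criteria are met, drug stops and End of Treatment procedures follow.
- **The purpose.** Section 9.3 says: "Patients with apparent failure-to-improve to a stable dose of study drug will be taken off study drug". Section 9.2 argues that after titration "an approximate 2-week window on stable drug dose should be sufficient for the drug to start eliciting a beneficial effect".
- **Interruptions.** Section 9.7.1 allows a dose hold at the investigator's discretion; its length is discussed with the Medical Monitor and no maximum is given. Section 9.7.3 lets a patient who has missed more than 6 consecutive doses continue if the Medical Monitor authorises it, with once-daily dosing for the first 3 days.
- **The score.** Worst Itch NRS covers the past 24 hours (Section 9.7.7.1).
- **The endpoint.** The frequency and timing of failure to improve is a secondary endpoint (Section 5.2).

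**The concern.** A scheduled visit can fall inside a hold or the once-daily restart. The 24-hour score then describes itch without drug, or on half the daily dose. The baseline is itself an off-drug score: "Patients can enroll into TR03ext and receive drug as early as approximately 2 weeks" after the last TR03 dose. A score taken during a hold therefore compares off-drug itch with off-drug itch and says little about response.

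At stake are three things. A patient who was benefiting can lose treatment permanently because itch came back when drug was withheld, which if anything suggests a drug effect. That patient is then counted as a failure to improve. And the patient's exposure ends early, in a study whose primary endpoint is adverse events in Treatment Weeks 5-50.

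**Working it through.** **Text.** The protocol gives no figure to reproduce, so the first check sets the places side by side.

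1. Synopsis and footnote 6: the stop applies at every Treatment Visit from TV3 and depends only on the score.
2. Section 9.3: failure to improve is judged on a stable dose. A patient on hold or on the once-daily restart is not taking one.
3. Sections 9.7.1 and 9.7.3: the Medical Monitor is involved in hold length and in the restart, but neither section suspends the test or lets the Monitor waive the stop.

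**Size.** From the protocol: TV3 to TV13 fall in Treatment Weeks 5, 9, 13, 17, 21, 26, 30, 34, 38, 42 and 46 for patients entering at Visit 1a. That gives nine intervals of 28 days and one of 35 (TV7 to TV8). The maximum is 60 patients. Everything else is assumed: interruption timing uniform, visits not rescheduled, holds of 7 or 14 days, 3 to 12 patients with one interruption each, and a 10-50% chance that itch is then at or above baseline.

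Chance that the whole 24 hours before a visit lies in an affected window of w days = (w − 1)/interval:

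| Interruption | w (days) | 28-day interval | 35-day interval |
|---|---|---|---|
| 7 missed doses (3.5 days) + 3 once-daily days | 6.5 | 5.5/28 = 19.6% | 5.5/35 = 15.7% |
| 7-day hold | 7 | 6/28 = 21.4% | 6/35 = 17.1% |
| 14-day hold | 14 | 13/28 = 46.4% | 13/35 = 37.1% |

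Multiplying the 28-day column by 0.1 to 0.5 gives the chance that one interruption leads to such a stop: 2.0-9.8%, 2.1-10.7% and 4.6-23.2%.

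Expected patients stopped:
- low: 3 × 0.196 × 0.1 = 0.06
- high: 12 × 0.464 × 0.5 = 2.8, and 2.8/60 = 4.6%

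**Load of a 14-day deferral.** Share of interruptions that defer a test = (w + 14)/28: 20.5/28 = 73%, 21/28 = 75%, 28/28 = 100% (59%, 60% and 80% in the 35-day interval). Deferred tests in all: 3 × 0.73 = 2.2 to 12 × 1.0 = 12.

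**Can one interruption defer two tests?** With ±3-day windows (Section 9.6), visits can be 28 − 3 − 3 = 22 days apart. An interruption under way at one visit reaches the next visit's 14-day look-back if it runs more than 22 − 14 = 8 days beyond the first. So an interruption longer than about 8 days can touch two tests.

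**The case against.** **Section 11.1 is unseen.** Section 9.2 and the visit steps send the reader there for the criteria, and the text at hand ends at the heading of Section 10.2. This stands. A reader might infer that the protocol has no exception anywhere, or that the TV3-TV13 steps confirm an unconditional rule; neither is supported, since those steps apply whatever Section 11.1 says. The evidence is the synopsis and footnote 6, which would need aligning with any exception there.

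**The 2-week window in Section 9.2 mainly explains why testing starts at TV3.** This also stands; it should not be read as a condition at every visit. Section 9.7.3 moreover uses stable dose as the name of a study phase, which softens the wording of Section 9.3. Section 9.3 still ties failure to improve to a stable dose, and someone on hold is not taking one.

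**Visits can be moved.** A shift of up to 3 days can often avoid the short restart, so the overlap figures are on the high side for short interruptions. It cannot avoid a hold of a week or more around the planned date.

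**Itch may not return.** A reader might infer that an interrupted patient will be stopped. The protocol does not support that: treated patients "may still have either reverted to their original pruritic conditions or may have a residual anti-pruritic effects from the drug treatment" about 2 weeks after dosing, and the design "anticipates potential sustained anti-pruritic effect that may outlast the actual dosing of study drug in TR03". Neither statement addresses 3.5 days off drug or once-daily dosing, so the chance is unknown.

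**A strict stop is a cautious choice for a drug with opioid properties.** Partly accepted. But Section 9.2 aims at patients who show no reduction in itch, and a patient tested at TV4 or later has already passed each earlier test applied.

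**Conclusion.** The point holds in a limited form. As stated in the synopsis and footnote 6, the rule can permanently stop a patient on a score taken off drug or on half the daily dose, and count that patient as failing to improve, which does not fit the stable-dose wording of Section 9.3.

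The effect is small: 0.06 to 2.8 expected stops, so probably 0 to 3 of at most 60 patients. That range rests wholly on the assumed interruption and reversion rates, and on random timing without rescheduling; the upper end combines every maximum. A reader might infer that the secondary endpoint is materially distorted. That is not supported: few patients are involved, the endpoint is descriptive and no formal testing is planned. The change is minor and mainly protects the individual patient.

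**What to change.** Add to the synopsis, to footnote 6 and, if not already there, to Section 11.1:

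> If a dose hold, or a run of more than 6 consecutive missed doses including its 3-day once-daily restart, fell within the 14 days before a Treatment Visit, the failure-to-improve test is not applied at that visit and is applied at the next one. It may not be deferred at two consecutive visits without Medical Monitor agreement.

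The 14 days borrows the 2-week period in Section 9.2. The Medical Monitor clause covers interruptions long enough to reach two visits. Dose reductions do not defer the test, because the patient is still taking drug twice daily.

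Cost: a short insertion in up to three places. Dosing can be checked from the Dosing Diary and the drug accountability already planned. On the assumptions above, about 2 to 12 tests would be deferred across the study. The downside is that a few patients without benefit stay on drug about 4-5 weeks longer, or to the end of treatment if the test is deferred from TV13, under the same safety visits.

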9.7.2 Down-Titration

Down-titration is not permitted except as discussed in [Section 9.7.1](#).

9.7.3 Multiple Missed Doses

If a patient misses multiple doses of the Study Drug, please follow the procedures below. In no case should patients take additional doses of Study Drug to make up for missed doses. If Study Drug is re-started after missed doses, the patient should be instructed to take Study Drug from the tablets designated for the visit during which Study Drug is being re-started rather than from the visits during which Study Drug doses were missed.

- **During the Titration Period**

If a patient misses 3 (or more) consecutive doses, please contact the study Medical Monitor.

- **During the Stable Dose Period**

If a patient misses 6 (or more) consecutive doses, please contact the study Medical Monitor. If authorized by the Medical Monitor, patients who miss more than 6 consecutive doses may be allowed to continue on study. In such situations, patients should receive the Study Drug only once daily (i.e., the AM or PM dose only) for the first 3 days before returning to the full (BID) target dose.

9.7.4 Overdose

The effects of nalbuphine may be reversed with opioid antagonists such as naloxone. Please see Guidance to the Investigator section of the Investigator Brochure for additional information.

9.7.5 Treatment Compliance

Returned study drug tablets will be used to assess compliance at each visit. Medication compliance will be recorded on the CRF for each designated visit (See [Appendix 1](#)). Patient compliance with the study dosing schedule will be assessed as part of the planned study analyses.

9.7.6 Rescue Medications, Concomitant Medications, Prohibited Medications, and Pre-Medications

9.7.6.1 Rescue Medications

A secondary objective of the study is to quantitate the number of days of rescue medication use for itching during the course of nalbuphine HCl ER treatment. Rescue medications will be defined as those drugs, when used for the purpose of treating itch, that were required to be washed out prior to entry into TR03 (See [Table 9](#)). For the purposes of this study, any UV light treatment received will also be defined as a rescue medication.

If a medication is prescribed for chronic anti-pruritic use of greater than 2 weeks, the subject should be discontinued (see [Section 11.2](#)).

9.7.6.2 Concomitant Medications

Any medication taken by a patient following the signing of informed consent during the course of the study and the reason for use of the medication will be recorded on the case report form (CRF). Each patient will be instructed to report the use of all medication to the Investigator, including over-the-counter [OTC] medications, herbal medications, vitamins, and nutritional supplements. Patients will also be instructed about the importance of not taking any new medications during the study (including OTC medications) without consulting the Investigator.

9.7.6.3 Prohibited Medications

Initiating use of opiate medications during the study should be done with caution with assessment of the patient for potential additive opiate AEs. If an enrolled patient requires daily treatment with opioid medications during the study (e.g., for post-surgical pain), please contact the Medical Monitor. Use of acetaminophen, non-steroidal anti-inflammatory medications, and aspirin is permitted. If an opioid medication is introduced in anticipation for chronic use of greater than 2 weeks, the subject should be discontinued.

Concomitant use of opioid antagonists (e.g. naloxone, naltrexone) are also prohibited during the study, unless required for urgent reversal of opioid adverse effects or opioid overdose.

Use of all other investigational drugs are prohibited during the study. A subject who initiates an investigational drug during the study should be discontinued.

If the patient is prescribed a medication(s) included on the list of those with a known risk of Torsade de Pointes (see [Section 9.7.8](#), Safety Assessments, for hyperlink to the CredibleMeds Filtered QTDrug List for cardiovascular related prohibited medications with a known associated risk of Torsade de Pointes), contact the Medical Monitor.

